## **6 Sample Size**

The sample size for this study is limited by the early stage of the product concept/testing and is designed to evaluate preliminary safety data but not designed to show statistically significant differences between groups. Given the small number of subjects per group, the precision of our estimate for adverse events is limited. For example, using binomial probability formulae for no observed adverse events within the 8 subjects yields a 95% exact confidence interval of 0-31%. Follow-on studies evaluating seemingly safe and immunogenic doses will be required with larger numbers of subjects in order to better define the safety profile.

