## **5 Study Methods**

This is an open-label Phase 1 clinical trial of CssBA±dmLT in which a total of 50 subjects will receive three vaccinations via IM injection on days 1, 22, and 43 (See Table 2). Dose escalation of CssBA from 5µg to 15µg to 45µg, and dmLT from 100 to 500ng will take place as outlined below. Group A is considered a pilot group in which CssBA and dmLT will be administered separately. All 3 doses will be administered and subjects monitored for safety 7 days after the third vaccination, prior to the enrollment of subjects in Group B.

The decision to advance to the next group will be based solely on the safety assessment. A dose level with no occurrence of stopping criteria will prompt moving to the next higher level. All safety data will be summarized and reviewed with the SRC prior to advancing to dose escalation.

Approximately one week after the first group (Group A) receives the third vaccination dose (Day 49), an interim Safety Report will be prepared by the PI and Study Statistician for review by the SRC. The content of the report will be agreed upon by the PI and the SRC and will include, but not be limited to, all adverse events (solicited, unsolicited, expected and unexpected) as well as relevant safety endpoints. Advancement to Group B will be based entirely on this safety assessment. The SRC's concurrence to advance to the next group will be made and provided in written format. This process will be repeated after groups B, C, and D before enrollment for the next group.

dmLT will be administered at the 500 ng dose in groups D and E if no significant reactogenicity is observed in Group C.

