**Table 2. Study Design of Phase 1 Clinical Trial of Intramuscularly Administered CssBA with dmLT (N=50)**

Group	N	Route	CssBA (µg)	dmLT (ng)
A	5	IM	5	0
	5	IM	0	100
B	10	IM	5	100
C	10	IM	5	500
D*	10	IM	15	100/500
E*	10	IM	45	100/500

\*Plan to proceed with 500ng dose; however, if there is an aberrant safety signal in Group C, will proceed with the 100 ng dose (presuming no prior signal in Group B)

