### 6.3 Confidence Intervals and p-values

Rates of all AEs will be summarized with point estimate for percentage and 95% confidence intervals. Immunological outcomes will also be summarized in a tabular format and graphed to demonstrate kinetics of response. Qualitative (responder rates) and quantitative assessments (log transformed values) will be analyzed. Median increases (fold rises) of antibody concentrations and seroconversion rates will be calculated along with their 95% confidence intervals. Geometric mean titers will also be determined and presented with their 95% confidence intervals. All statistical tests will be interpreted in a two-tailed fashion using an  $\alpha = 0.05$ .

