The proportion of all subjects with each AE will be summarized with point estimate for percent and 95% confidence intervals calculated using valid asymptomatic and/or exact binomial estimates. Summary tables will be created which will describe the number and percentage of subjects who experience each adverse event. In addition, tables will be prepared to list each adverse event, the number of subjects experiencing an event at least once, and the proportion of subjects with adverse event(s). Adverse events will be divided into defined severity grades (mild, moderate, severe, or potentially life-threatening). The tables will also divide the adverse events by severity and related (definite, probable, possible) or unrelated (unlikely, not related) to the investigational product.

All subjects who receive vaccination will be included in the safety analysis. Adverse event data will be listed individually and summarized by body system and preferred terms within a body system for each treatment group. Serious and/or unexpected AEs will also be discussed on a case-by-case basis. For the tabulation of the AEs by body system, a subject will be counted only once in a given body system. For example, a subject reporting nausea and diarrhea will be reported as one subject, but the symptoms will be listed as two separate AEs within the class. Therefore the total number of AEs reported within a body system may exceed the number of subjects within the body system reporting AEs.

Rates of all adverse events will be analyzed by Pearson's Chi-square test (or Fisher's exact test if assumptions are not met for Pearson's Chi-square) to compare dose levels. Summary tables will be created which will indicate the number of subjects who experienced events. Vaccine-related events (probably or possibly related) will be tabulated by study group. In addition, tables will be prepared to list each adverse event, the number of subjects in each treatment group who experienced an event at least once, and the rate of subjects with adverse event(s). Adverse events will be divided into defined severity grades (mild, moderate, severe). The tables will also divide the adverse events by severity and relationship to the investigational product. All immunized subjects will be included in the safety analysis.

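### The one precision figure in SAP Section 6 (0-31% for no events in 8 subjects) matches no group in Table 2, and as a two-sided exact interval it belongs to 10 subjects, not 8

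*SAP*

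**What the plan says.** Section 6 (Sample Size) explains that the trial's size follows from the early stage of the product and that it is not meant to detect differences between groups. It concedes that adverse event rates will be estimated imprecisely, and gives one example: "no observed adverse events within the 8 subjects yields a 95% exact confidence interval of 0-31" percent. It does not say whether the interval is one-sided or two-sided.

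The group sizes are in Section 5. The text says that "a total of 50 subjects will receive three vaccinations via IM injection on days 1, 22, and 43", and that "Group A is considered a pilot group in which CssBA and dmLT will be administered separately". Table 2 lists two Group A arms of 5 (CssBA alone, dmLT alone) and Groups B, C, D and E with 10 each.

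On conventions, Section 6.3 states "All statistical tests will be interpreted in a two-tailed fashion using an" alpha of 0.05. That rule is about tests. For adverse event proportions, Section 7.1.1 plans "95% confidence intervals calculated using valid asymptomatic and/or exact binomial estimates".

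**The concern.** The figure fails two simple checks. Its denominator is not the size of any group in the trial. Its upper limit is also not what the usual two-sided exact interval gives for that denominator.

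Safety is the only primary objective, and this is the only number in the SAP that tells a reader how much a group without events can show. A reader who takes 31% as the general precision would think a clean Group A arm more informative than it is. Those arms have 5 subjects each, and the interim safety report in Section 10 presents them separately as A-1 and A-2.

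**Working it through.** **Inputs.** Events x = 0, n = 8, 95% exact, stated limit 31% (Section 6). Actual sizes n = 5 and n = 10 (Table 2).

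**Formula.** With no events the lower limit is 0. The exact upper limit p solves (1 − p)^n = a, so p = 1 − a^(1/n). A two-sided 95% Clopper-Pearson interval uses a = 0.025. A one-sided 95% bound uses a = 0.05.

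**Reproducing the stated 31%.**
- 0/8, two-sided: 1 − 0.025^(1/8) = 1 − 0.6306 = 36.9%. This does not reproduce it.
- 0/8, one-sided: 1 − 0.05^(1/8) = 1 − 0.6877 = 31.2%. This does.
- 0/10, two-sided: 1 − 0.025^(1/10) = 1 − 0.6915 = 30.8%. This does.

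Direct check: if the true rate were 31%, the chance of no event in 8 subjects would be 0.69^8 = 0.051. That is the 5% of a one-sided bound, not the 2.5% of a two-sided interval.

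Other two-sided methods at 0/8 give 32.4% (Wilson), 37.2% (Agresti-Coull) and 26.2% (Jeffreys). The mid-p interval solves 0.5 × (1 − p)^8 = 0.025, which is the same equation as the one-sided bound, and so also gives 31.2%.

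**What the trial's own groups give with zero events.**

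| Group | n | Two-sided exact 95% upper limit | One-sided exact 95% upper bound |
|---|---|---|---|
| Not in Table 2 | 8 | 36.9% | 31.2% |
| B, C, D, E | 10 | 30.8% | 25.9% |
| A-1, A-2 | 5 | 52.2% | 45.1% |

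On the two-sided convention 31% fits the groups of 10. On the one-sided convention it fits no planned group. In a 5-subject arm, a true event rate of 50% would still give no event with probability 0.5^5 = 0.031, which is above 0.025, so such a rate cannot be excluded.

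**Could 10 become 8?** Section 6.1.1 puts everyone who received at least one dose in the safety population, and the SAP states no dropout or evaluability allowance that would reduce 10 to 8.

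**The case against.** The best defence is that 31% can be obtained from 0/8. Sidedness is not stated, the lower limit is 0 under either convention, and a one-sided 95% exact bound (or a mid-p interval) gives 31.2%. The two-tailed rule in the SAP is written for tests, not intervals. This stands to the extent that the SAP cannot show whether the slip is in the 8 or in the unstated convention, so it would be too strong to call 31% a plain miscalculation. It does not rescue the sentence. The SAP names neither a one-sided bound nor mid-p, and a one-sided 95% bound is the upper end of a two-sided 90% interval. Under either method the real groups would give 25.9% and 45.1%, and a group of 8 would still not exist.

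The other objections concern consequence, and they largely stand:
- A reader might infer that the sample size rests on a faulty calculation. Section 6 bases the size on the product's early stage and offers the interval only as an illustration.
- A reader might infer that moving from Group A to Group B is affected. Sections 5 and 10 rest advancement on stopping criteria and the safety committee's review, and neither uses a confidence limit.
- A reader might say the SAP misstates the precision of the 5-subject arms. It makes no claim about them; it leaves the figure out.
- A reader might link this to the choice of interval in Section 7.1.1. That section allows "calculated using valid asymptomatic and/or exact binomial estimates", which is a separate question of method and has no bearing on whether the Section 6 figure is right.

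**Conclusion.** The example in Section 6 does not fit the trial as written. Its n of 8 matches no group, and the two-sided exact limit at that n is 36.9%, about 6 percentage points above the stated 31%. For Groups B to E, 40 of the 50 subjects, the printed 31% is correct once n reads 10. For the two Group A arms the limit is 52.2%, about 21 points above the only figure a reader is given.

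The comparison with 36.9% assumes that an exact 95% interval means two-sided Clopper-Pearson. This is the usual meaning and agrees with the SAP's two-tailed convention, although the SAP does not say so for intervals. The mismatch between n = 8 and Table 2 does not depend on that assumption.

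The point is minor. It corrects a statement about precision and changes no sample size, analysis population, planned analysis or escalation decision.

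**What to change.** Replace the example in Section 6 with:

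*No observed adverse events gives an exact (Clopper-Pearson) two-sided 95% CI of 0-31% in a 10-subject group (B-E) and 0-52% in each 5-subject arm of Group A.*

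This settles n, method and sidedness together and ties the figures to Table 2. It costs one sentence and needs no new data. The only drawback is that the SAP will now show a less favourable figure for the Group A arms.

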### **6.1 Purpose of the analyses**

The primary study objective is to evaluate the safety of CssBA ± dmLT given by IM injection  
Analysis Populations

### 6.1.1 Safety Population

All subjects that receive one or more doses of the investigational product(s) will be included in the safety analysis. Adverse events will be listed individually and summarized by body system and preferred terms within a body system for each treatment group. Serious and/or unexpected AEs will also be discussed on a case-by-case basis.

### 6.1.2 Immunology Populations

Analyses will include both qualitative (responder rates) and quantitative results ( $\log_{10}$  transformed values). All subjects that receive at least 2 doses of the investigational product and have requisite post-vaccination samples collected will be included in the analysis.

### 6.2 Missing Data

All subjects selected to participate in the study and meet the necessary population requirements will be included in the safety and/or immunology analysis. Data will be assumed to be missing at random and missing data points will be excluded from analysis.

### 6.3 Confidence Intervals and p-values

Rates of all AEs will be summarized with point estimate for percentage and 95% confidence intervals. Immunological outcomes will also be summarized in a tabular format and graphed to demonstrate kinetics of response. Qualitative (responder rates) and quantitative assessments (log transformed values) will be analyzed. Median increases (fold rises) of antibody concentrations and seroconversion rates will be calculated along with their 95% confidence intervals. Geometric mean titers will also be determined and presented with their 95% confidence intervals. All statistical tests will be interpreted in a two-tailed fashion using an  $\alpha = 0.05$ .

## 7 General Considerations

### 7.1 Analysis Population

#### 7.1.1 Safety Analyses

All AE's will be assessed for severity by the investigator. Essential in this assessment is the medical and clinical considerations of all information surrounding the event including any medical interventions required. Each event will be assigned one of the following categories: mild, moderate, severe, or life-threatening. The criteria below may be used for any symptom not included in the grading scale.

The eCRFs for AEs will reflect only the highest severity for continuous days and event occurred.

Mild	Grade 1	Does not interfere with routine activities; minimal level of discomfort
Moderate	Grade 2	Interferes with routine activities; moderate level of discomfort
Severe	Grade 3	Unable to perform routine activities; significant level of discomfort
Potentially life-threatening	Grade 4	Hospitalization or ER visit for potentially life-threatening event

FDA guidelines for toxicity will be followed; however if a subject is evaluated in an emergency room for nonlife threatening illness or symptoms (ie, visits emergency department on weekend for mild

problems because the physician's office is closed), the information from that visit will be reviewed and severity of the adverse event will be assessed according to the subject's clinical signs and symptoms.

As defined by the ICH guideline for GCP, the term "severe" is often used to describe intensity (severity) of a specific event (as in mild, moderate, or severe myocardial infarction); the event itself however, may be of relatively minor medical significance (such as severe headache). This is not the same as "serious," which is based on subject/event outcome or action criteria usually associated with events that post a threat to the subject's life or functioning. Seriousness (not severity) serves as a guide for defining regulatory obligations.

The proportion of all subjects with each AE will be summarized with point estimate for percent and 95% confidence intervals calculated using valid asymptomatic and/or exact binomial estimates. Summary tables will be created which will describe the number and percentage of subjects who experience each adverse event. In addition, tables will be prepared to list each adverse event, the number of subjects experiencing an event at least once, and the proportion of subjects with adverse event(s). Adverse events will be divided into defined severity grades (mild, moderate, severe, or potentially life-threatening). The tables will also divide the adverse events by severity and related (definite, probable, possible) or unrelated (unlikely, not related) to the investigational product.

All subjects who receive vaccination will be included in the safety analysis. Adverse event data will be listed individually and summarized by body system and preferred terms within a body system for each treatment group. Serious and/or unexpected AEs will also be discussed on a case-by-case basis. For the tabulation of the AEs by body system, a subject will be counted only once in a given body system. For example, a subject reporting nausea and diarrhea will be reported as one subject, but the symptoms will be listed as two separate AEs within the class. Therefore the total number of AEs reported within a body system may exceed the number of subjects within the body system reporting AEs.

Rates of all adverse events will be analyzed by Pearson's Chi-square test (or Fisher's exact test if assumptions are not met for Pearson's Chi-square) to compare dose levels. Summary tables will be created which will indicate the number of subjects who experienced events. Vaccine-related events (probably or possibly related) will be tabulated by study group. In addition, tables will be prepared to list each adverse event, the number of subjects in each treatment group who experienced an event at least once, and the rate of subjects with adverse event(s). Adverse events will be divided into defined severity grades (mild, moderate, severe). The tables will also divide the adverse events by severity and relationship to the investigational product. All immunized subjects will be included in the safety analysis.

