### Results

**Table 3: Demographic characteristics of study subjects**

Characteristic	Participant (n =)	Screened (Not Enrolled)
Mean Age (sd)*	0	0
Age range	-	-
Gender (%)		
Male	0	0
Female	0	0
Race/Ethnicity		
African-American	0	0
Caucasian	0	0
Asian-American	0	0
Other	0	0

\*Measured in mean (standard deviation)

**Table 4:** Baseline characteristics of study participants (by cohort)

Cohort	A		B	C	D	E
	A-1	A-2				
Age a						
Gender [N (%)]						
Male						
Female						
Race/Ethnicity [N (%)]						
African-American						
White						
Asian						
Other						
LT IgA						
LT IgG						
CS6 IgA						
CS6 IgG						

a Presented as mean (standard deviation) or median (interquartile range)

**Table 5.** Safety profile of all adverse symptoms coded as ‘related’ to vaccine following vaccination [n(%)] (Groups compared using a Chi-squared analysis)

AE	Cohort A			Cohort B			Cohort C			Cohort D			Cohort E		
Dose	1	2	3	1	2	3	1	2	3	1	2	3	1	2	3
AE1															
AE2															
AE#															

**Table 6.** Safety profile of all adverse symptoms coded as ‘unrelated’ to vaccine following vaccination [n(%)] (Groups compared using a Chi-squared analysis)

AE	Cohort A			Cohort B			Cohort C			Cohort D			Cohort E		
Dose	1	2	3												
AE1															
AE2															
AE#															

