**A-1 (5 µg CssBA)**

**A-2 (100 ng dmLT)**

**B (5 µg CssBA + 100 ng dmLT)**

**C (5 µg CssBA + 500 ng dmLT)**

**D (15 µg CssBA + 100 or 500 ng dmLT)**

**E (45 µg CssBA +100 or 500 ng dmLT)**

**Vaccine Dose** (Circle one) **1 2 3**

**N =**

Cumulative summary of adverse signs and symptoms								
Symptoms	N (%) of volunteers exhibiting each adverse event							
	Grade 1		Grade 2		Grade 3		Grade 4	
	R	NR	R	NR	R	NR	R	NR
Local site pain								
Local site pruritis								
Vaccine site rash/eruption								
Vaccine Site Swelling (As reported by subject)								
Vaccine Site Tenderness								
Fever (subjective or objective)								
Headache								
Loose stools								
Arthralgia								
Myalgia								
Malaise								

R: Any sign or symptom coded as at least possibly related to the study product.

NR: Any sign or symptom coded as unrelated to the study product.

Note: The highest severity of an adverse event recorded for each subject (by relationship strata).

**COMBINED INTERIM SAFETY REPORT FOR 3-DOSE SERIES:  
Vaccine Cohort (Circle one)**

- A-1 (5 µg CssBA)**
- A-2 (100 ng dmLT)**
- B (5 µg CssBA + 100 ng dmLT)**
- C (5 µg CssBA + 500 ng dmLT)**
- D (15 µg CssBA + 100 or 500 ng dmLT)**
- E (45 µg CssBA +100 or 500 ng dmLT)**

N =

Cumulative summary of adverse signs and symptoms								
Symptoms	N (%) of volunteers exhibiting each adverse event							
	Grade 1		Grade 2		Grade 3		Grade 4	
	R	NR	R	NR	R	NR	R	NR
Local site pain								
Local site pruritis								
Vaccine site rash/eruption								
Vaccine Site Swelling (As reported by subject)								
Vaccine Site Tenderness								
Fever (subjective or objective)								
Headache								
Loose stools								
Arthralgia								
Myalgia								
Malaise								

R: Any sign or symptom coded as at least possibly related to the study product.

NR: Any sign or symptom coded as unrelated to the study product.

Note: The highest severity of an adverse event recorded for each subject (by relationship strata).

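### The SAP disclaims cohort comparison, yet orders a test of every adverse event between dose levels at two-sided 0.05 without adjustment or a descriptive label

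*SAP*

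**What the plan says.** - **Purpose.** The only primary objective (Section 4.1) is to evaluate safety, and no hypothesis is attached. Section 3 says the study is meant for estimation rather than for comparing cohorts, then says the comparisons will be made all the same. Section 6 adds that the trial is "not designed to show statistically significant differences between groups".
- **What is tested.** Section 7.1.1: "Rates of all adverse events will be analyzed by" Pearson's chi-square, or by Fisher's exact test where the conditions for Pearson's test fail, with the stated aim of comparing dose levels. The same section asks for AE percentages with 95% confidence intervals.
- **Layout.** The shells for Tables 5 (related) and 6 (unrelated) in Section 9 have one row per AE and three dose columns for each of Cohorts A to E. Both captions read "Groups compared using a Chi-squared analysis".
- **Level.** Section 6.3: "All statistical tests will be interpreted in a two-tailed fashion using an" alpha of 0.05. Section 3 says the same.
- **Multiplicity.** Section 3 lists four post-hoc methods for contrasts between cohorts and chooses none. Nothing covers multiplicity across AEs, doses or relatedness classes.

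**The concern.** The plan disclaims comparison and then orders many comparisons, each read at the full 0.05. It gives no rule for reading, say, a p-value of 0.03 for one symptom after the second dose. Since safety is the sole primary objective, these tables carry the trial's main result. A chance difference on one symptom could be reported as a dose-related signal. A non-significant result could be reported as no difference, although cohorts of 10 cannot support that. Section 4.2 also aims to identify a safe and immunogenic dose for a later trial, so such a reading could carry forward.

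**Working it through.** **1. The plan's only design figure.** Section 6 gives 0-31% as the exact 95% interval for no events in 8 subjects. The upper limit for 0 of n is 1 − tail^(1/n).
- n = 8, one-sided 5% tail: 1 − 0.05^(1/8) = 31.2%, which matches.
- n = 8, two-sided: 1 − 0.025^(1/8) = 36.9%, which does not match.
- n = 10, two-sided: 1 − 0.025^(1/10) = 30.8%, which matches for the cohort size in Table 2.

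The SAP states no power and no family-wise error rate, so there is no further figure to reproduce.

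**2. Inputs.** Five cohorts of 10 (Section 5, Table 2, with Group A's two subgroups of 5 merged as in Tables 5 and 6). Eleven symptoms (interim form, Section 10). Alpha 0.05 two-sided (Sections 3 and 6.3). Three doses give 11 × 3 = 33 tests per table. AE rates and within-subject correlation are **assumptions**, because the SAP gives neither.

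**3. Which test applies.** With 10 per cohort and m events in total, the expected counts per cohort are m/5 events and (50 − m)/5 non-events. Both reach 5 only when m = 25. Under the usual expected-count rule nearly every table therefore goes to Fisher's test, and the figures below use the exact test.

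**4. Size of one test, and of the family.** The exact size comes from full enumeration of the 5 × 2 tables with equal risk. For k independent tests, the chance of at least one p ≤ 0.05 is 1 − (1 − size)^k.

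| Assumed rate, every AE | Size of one test | k = 11 | k = 33 |
|---|---|---|---|
| 2% | 0.0020 | 2% | 6% |
| 5% | 0.0095 | 10% | 27% |
| 10% | 0.0168 | 17% | 43% |
| 20% | 0.0283 | 27% | 61% |
| 30% | 0.0408 | 37% | 75% |
| 50% | 0.0443 | 39% | 78% |

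Worked line at 30%: 1 − (1 − 0.0408)^11 = 0.37 and 1 − (1 − 0.0408)^33 = 0.75. The nominal ceiling at exactly 0.05 per test is 1 − 0.95^11 = 43% and 1 − 0.95^33 = 82%. The exact test is conservative, which is why the table lies below that ceiling.

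**5. Allowing for correlation within subjects.** Simulation with a shared latent factor per subject, identical risk in all cohorts and Fisher's exact test, 800 replicates per setting. Each cell shows correlation 0 / 0.5 / 0.8.

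| Assumed rates | 11 tests | 33 tests |
|---|---|---|
| Mixed, 5-60% | 25 / 23 / 23% | 58 / 51 / 38% |
| All 10% | 17 / 17 / 14% | 42 / 38 / 26% |
| All 30% | 37 / 32 / 23% | 75 / 64 / 44% |

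Correlation lowers the figures but does not remove the excess over 5%.

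**6. What a non-significant result means.** Exact power of one omnibus Fisher test over five cohorts of 10 is 34% if true risk rises 10, 20, 30, 40, 50% across cohorts, and 9% if it rises 10, 15, 20, 25, 30%.

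**The case against.** The strongest defence is that this is a 50-subject, open-label Phase 1 study whose plan says it estimates rather than compares. Dose advancement rests on stopping criteria and safety committee review (Sections 5 and 10), and the interim forms contain counts by grade and relatedness with no tests. That stands, and it limits the harm to the reading of the final report.

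A reader might infer that the primary objective is defective because no single deciding safety comparison is named. The document does not support this: an estimation study needs none, and the estimates with intervals are already specified. A newly named test would also be weak. With a true risk of 40% in one cohort and 10% in the other four, the omnibus exact test has 28% power.

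A reader might also infer that a false positive is to be expected at some fixed frequency. That too is unsupported, because every such figure rests on assumed AE rates.

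Three further limits are fair. The count of 33 comes from sample shells that Section 9 says may be modified, and Section 7.1.1 itself does not prescribe a test after each dose. The 11 symptoms come from the interim form, and unsolicited AEs would add to them. Table 6 has some use, since relatedness is judged by investigators in an open-label trial and unrelated events may reveal misattribution.

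None of this supplies the missing sentence on how an AE p-value is to be read.

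**Conclusion.** The point holds as an inconsistency between the stated purpose and the ordered analysis. Every AE rate is tested between dose levels at 0.05, without adjustment across AEs and without a descriptive label, in a study that says it does not aim to compare.

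With identical risk in five cohorts of 10, 11 symptoms and assumed rates within 5% to 60%, the chance of at least one p ≤ 0.05 is roughly 15-40% with one test per symptom and roughly 25-75% with one test per symptom and dose. At the bottom edge, with all 11 rates at 5%, the once-per-series figure is 10%. If every rate were 2%, the figures are about 2% and 6%. These values depend on the assumed rates, the correlation and the per-dose reading of the shells. The textual inconsistency does not. No dosing decision is affected. This is an inexpensive improvement to the plan and not a flaw in the design.

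**What to change.** In Section 7.1.1, state that AE results are presented by cohort as counts, percentages and exact 95% confidence intervals. Add that any between-cohort p-value for an AE is nominal, exploratory and unadjusted, and supports neither a claim of a difference nor a claim of no difference. In Tables 5 and 6, delete "Groups compared using a Chi-squared analysis" or replace it with: *nominal Fisher's exact p-values, exploratory*. No new primary safety test is needed.

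The cost is one added statement and two captions. All counts and intervals stay. What is given up is any significance claim for a single AE.
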